2.3 Exploratory Objectives & Endpoints

2.3.1 Assess safety, tolerability and activity of nivolumab and ipilimumab in non-ACC malignant salivary gland tumors (MSGT's) using CBR, ORR, PFS, OS.

2.3.2 To assess the predictive value of genomic aberrations observed upon comprehensive genomic profiling of the tumor DNA derived from archival tumor tissue, if available, or blood from patients with recurrent or metastatic ACC and non-ACC MSGTs.

2.3.3 Correlation between expression of PD-L1 and response to treatment will be explored in all patients enrolled in the study.

2.3.4 Correlations between other markers of inflammatory/immune signature will be performed that may include but not be limited to PD-1, OX40, CD73, CD39, T cell immunoglobulin and mucin domain containing protein 3 (TIM3), GITRL, CTLA-4, CD3, CD4, CD8, protein tyrosine phosphatase receptor type C (CD45RO), forkhead box P3 (FOXP3), and granzyme by immunohistochemistry analysis and/or flow cytometry.

3.0 PATIENT ELIGIBILITY

The target population for this study is patients with metastatic/recurrent adenoid cystic carcinoma (ACC) and non-adenoid cystic carcinomas (non-ACC) of major or minor salivary glands who are not surgical or radiation candidates with evidence of disease progression. This study will be led by Northwestern University. At Northwestern University, there is no competing trial.

A total of 63 [43 patients with ACC plus 20 patients with non-ACC MSGT (exploratory group)] subjects will be needed for this trial. Approximately 2 potentially eligible patients are seen per month, and it is anticipated that at least 2 per month will be accrued. Potential patients may be referred to the Principal Investigator (PI) at Northwestern University.

Eligibility will be evaluated by the study team according to the following criteria. Eligibility waivers are not permitted. Subjects must meet all of the inclusion and none of the exclusion criteria to be registered to the study. Study treatment may not begin until a subject is registered. Please refer to Section 11 for complete instructions regarding registration procedures.

3.1 Inclusion Criteria

- 3.1.1 Patients must have histologically or cytologically confirmed metastatic/recurrent adenoid cystic carcinoma (ACC) of any anatomic site of origin or non-adenoid cystic carcinomas (non-ACC) of major or minor salivary glands
- 3.1.2 Patients must have evidence of disease progression and cannot be a candidate for curative surgical or radiation therapy.
NOTE: Disease progression is defined as one of the following occurring at least 6 months prior to study entry:
 - At least a 20% increase in radiologically or clinically measurable lesions
 - Appearance of any new lesions or
 - Symptomatic and/or deterioration in clinical statusNOTE: Palliative radiotherapy is permitted.
- 3.1.3 Patients may or may not have received prior therapy for their recurrent/metastatic disease.
NOTE: There is no limit to the number of prior systemic therapies for stage IV disease.
NOTE: Patients should not be a candidate for curative surgical or radiation therapy (palliative radiotherapy is permitted).
- 3.1.4 Patients must have measurable disease, defined as at least one lesion that can be accurately measured in at least one dimension in accordance with RECIST criteria v1.1.
NOTE: Scans must be \leq 28 days prior to study treatment.
- 3.1.5 Patients must be \geq 18 years old.
- 3.1.6 Patients must exhibit an ECOG status of 0-2.
NOTE: ECOG performance status 3 will be allowed only if thought to be directly secondary to adenoid cystic carcinoma disease by treating physician.

NU Study Number: NU 16N03
BMS Study Number: CA 209-802

3.1.7 Patients must have adequate organ and bone marrow function within 14 days prior to registration, as defined below:

- leukocytes $\geq 2,000/\text{mCL}$
- absolute neutrophil count $\geq 1,500/\text{mCL}$, regardless of transfusion or growth factor support
- platelets $\geq 100,000/\text{mCL}$, regardless of transfusion or growth factor support
- total bilirubin total bilirubin $\leq 1.5 \times$ institutional upper limit of normal (ULN) (except patients with Gilbert Syndrome or liver metastasis, who can have total bilirubin $\leq 3.0 \times$ ULN)
- AST(SGOT)/ALT(SPGT) $\leq 2.5 \times$ institutional upper limit of normal (ULN) (or ≤ 5 times ULN in case of liver metastasis)
- creatinine Serum creatinine of $\leq 3.0 \times$ ULN (upper limit of normal) or creatinine clearance $\geq 30 \text{ mL}/\text{minute}$ (using Cockcroft/Gault formula below):

$$\text{Female CrCl} = \frac{(140 - \text{age in years}) \times \text{weight in kg} \times 0.85}{72 \times \text{serum creatinine in mg/dL}}$$

$$\text{Male CrCl} = \frac{(140 - \text{age in years}) \times \text{weight in kg} \times 1.00}{72 \times \text{serum creatinine in mg/dL}}$$

3.1.8 Patients with history of central nervous system (CNS) metastases are eligible if CNS disease has been stable for at least 6 weeks prior to study registration in the opinion of the investigator and does not require corticosteroids (of any dose) for symptomatic management.

NOTE: Only patients with a known history or indication of CNS disease are required to have CNS imaging prior to study entry.

3.1.9 Females of childbearing potential (FOCBP) must have a negative serum or urine pregnancy test (minimum sensitivity 25 IU/L or equivalent units of HCG) ≤ 14 days prior to registration.

NOTE: A FOCBP is *any woman* (regardless of sexual orientation, having undergone a tubal ligation, or remaining celibate by choice) who meets the following criteria:

- *Has not* undergone a hysterectomy or bilateral oophorectomy
- *Has had* menses at any time in the preceding 12 consecutive months (and therefore has not been naturally postmenopausal for > 12 months)

3.1.10 FOCBP and men who are sexually active with FOCBP must agree to follow instructions for method(s) of contraception for the duration of treatment and the designated post-treatment period (see Appendix C for details on appropriate contraception methods)

3.1.11 Patients must have the ability to understand and the willingness to sign a written informed consent prior to registration on study.

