Sample Size	63 [43 patients with ACC plus 20 patients with non-ACC MSGT(exploratory group)]
Diagnosis & Key Eligibility Criteria	
Study population will consist of patients age 18 or older, Eastern Cooperative Oncology Group (ECOG) performance status 0-2, with metastatic/recurrent adenoid cystic carcinoma (ACC) of salivary and non-salivary gland origin, as well as non-adenoid cystic carcinomas (non-ACC) of major or minor salivary glands who are not surgical or radiation candidates with evidence of disease progression. Disease progression is defined as one of the following occurring within the 6 months prior to study entry:
 
 (1)At least a 20% increase in radiologically or clinically measurable lesions (2)Appearance of any new lesions or (3)Symptomatic and/or deterioration in clinical status 
Patients cannot have a history of clinically significant autoimmune diseases or a syndrome that requires systemic steroids or immunosuppressive agents. Patients on treatment with prednisone > 10mg daily or equivalent corticosteroid will be excluded.

NU Study Number: NU 16N03
BMS Study Number: CA 209-802

Treatment Plan	
Eligible patients will be started on nivolumab 240mg IV every 14 days for the first 8 doses and 480mg IV every 28 days starting with Cycle 2 Day 29 (1 cycle = 12 weeks / 84 days). Ipilimumab 1mg/kg IV will be given q 6 weeks starting at Cycle 1 Day 1 until disease progression, unacceptable toxicity or withdrawal of consent. Patients will have response assessments every 12 weeks (each cycle).
  
The diagram illustrates the treatment timeline across three cycles. Nivolumab is administered every 14 days (240mg for the first 8 doses, then 480mg every 28 days). Ipilimumab is given every 6 weeks (1mg/kg). Response assessments are conducted at weeks 13, 25, and 31. Cycle 1: Weeks 1-11. Cycle 2: Weeks 13-23. Cycle 3+: Weeks 25-35. Legend: Gray box = 240mg, Black box = 480mg, Dark Gray box = 1mg/kg.

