5.0 STUDY PROCEDURES

	Screening ¹	On Treatment ^{15,16} (1 cycle = 12 weeks / 84 days)														Off Treatment				
		Cycle 1 (Each visit -2/+4 days)							Cycle 2 (Each visit -2/+4 days)							Cycle 3+ (Each visit -2/+4 days)				
		Day of each cycle	1	15	29	43	57	71	1	15	29	43	57	71	1	15	29	43	57	71
	Weeks on study	1	3	5	7	9	11		13	15	17	19	21	23	25	27	29	31	33	35+
Informed Consent	X																			
Medical history	X																			
Physical exam ²	X	X		X					X		X			X		X			X	
ECOG status	X	X		X					X		X			X		X			X	
Adverse Events & ConMeds	X		X	X	X	X	X	X	X	X	X	X	X	X	X	X	X	X	X ¹⁷	
Scans (C/A/P/N) ^{3,4,5}	X ₃								X _{4,5}					X _{4,5}					X ₅	
CBC with diff ⁶	X	X	X	X	X	X	X	X	X	X	X	X	X	X	X	X	X	X	X	
Chemistry panel ⁷	X	X	X	X	X	X	X	X	X	X	X	X	X	X	X	X	X	X	X	
Amylase/Lipase ⁸	X	X		X					X		X			X		X			X	
TSH with reflex ⁹	X	X		X					X		X			X		X			X	
Echo/ECG ¹⁹	X ₁₉																			
Tissue for NGS ²⁰	X ₂₀	X ₂₀																		
Liquid biopsy ²¹	X ₂₁	X ₂₁							X ₂₁					X ₂₁					X ₂₁	
Pregnancy test ¹⁰	X	X																		
Nivolumab administration ¹¹	T	T	T	T	T	T	T	T	T	F	F	F	F	F	F	F	F			
Ipilimumab administration ¹²	X		X					X		X			X		X					
Study Labs ¹³	X											X ₁₃							X	
Tissue collection ¹⁴	X											X ₁₄								
Survival status																			X ₁₈	

T = 240mg nivolumab

F = 480mg nivolumab

¹ Screening procedures must take place within 28 days of registration unless otherwise specified (CBC with diff and Chemistry panel should be within 14 days of registration; scans should be within 28 days prior to starting treatment);

² Includes vital signs (pulse, blood pressure) and height (baseline only) and weight.

³ Imaging scans must include recurrent and/or metastatic disease, and must be within 28 days prior to starting study treatment. If a patient is scheduled to start treatment >28 days after the last scan, imaging must be repeated. Per treating investigator's discretion, images may include Neck, Chest, Abdomen, and Pelvis (or any combination to perform tumor assessment). Scans may be by CT, PET/CT or MRI (per treating investigator's

Initial Version: 11/23/2016

Amendment 8: 10/6/2022

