10.2 Sample Size and Accrual

A Simon two stage optimum Phase II design will be used ⁴⁶. The main outcome is median Progression Free Survival (PFS) as well as PFS at 6 and 12 months. The optimal two-stage design to test the null hypothesis that $P \leq 0.450$ versus the alternative that $P \geq 0.650$ has an expected sample size of 24.70 and a probability of early termination of 0.654. If the drug is actually not effective, there is a 0.048 probability of concluding that it is (the target for this value was 0.050). If the drug is actually effective, there is a 0.196 probability of concluding that it is not (the target for this value was 0.200). After testing the drug on 15 patients in the first stage, ACC accrual will be terminated if 7 or more patients are withdrawn from the study after <24 weeks of treatment for any reason other than withdrawal of consent (this includes toxicity, PD, intolerance etc.) If the trial goes on to the second stage, a total of 43 patients will be studied. If the total number responding (defined as stable disease or better) is less than or equal to 24, the drug is rejected. An exploratory group of 20 patients with MSGTs will be included in the study, in addition to the 43 patients mentioned above. They can be enrolled in any order within the total accrual of 63 patients and will not participate in statistical analysis. A separate safety analysis will take place; if >2 of the first 10 non-ACC patients are withdrawn after <24 weeks of treatment, non-ACC accrual will discontinue.

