10.3 Data Analyses Plans

Response rates and 95% confidence intervals will be calculated using exact binomial probability distributions for discrete outcomes. Progression-free survival and overall survival will be graphically depicted using Kaplan-Meier curves. Adverse events will be summarized descriptively using frequencies and percentages. Statistics will be given on type, severity, frequency and attribution of adverse events. Sample size considerations are described above.

An intention to treat analysis will be done. In a single group Phase II study, intention to treat means that all patients who are evaluated and registered for the study are followed and analyzed regardless of (a) whether they were subsequently found to be protocol ineligible and (b) the amount of study treatment (nivolumab/ipilimumab) they received. To calculate progression-free and overall survival in patients who received nivolumab/ipilimumab, times will be taken from the time of study registration. This definition parallels the definition of intention to treat in randomized clinical trials.

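### Inclusion criterion 3.1.2 and the Study Summary give opposite six-month windows for the qualifying progression

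*Combined protocol and SAP*

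**What the plan says.** Both the Study Summary (row on diagnosis and key eligibility) and Section 3.1.2 require evidence of progression. Both accept any one of three events: growth of at least 20% in measurable lesions, a new lesion, or symptomatic or clinical deterioration. They differ in when the event must have happened.

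- Section 3.1.2, note: "Disease progression is defined as one of the following occurring at least 6 months prior to study entry".
- Study Summary: "Disease progression is defined as one of the following occurring within the 6 months prior to study entry".

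Section 3.0 requires every inclusion criterion to be met before registration and adds: "Eligibility waivers are not permitted". Section 3.0 and the Study Schema also require progression, but give no time window.

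Three other places bear on the consequences. Footnote 1 of the Section 5.0 schedule says of screening that "scans should be within 28 days prior to starting treatment". Section 10.3 says registered patients are "followed and analyzed regardless of (a) whether they were subsequently found to be protocol ineligible". Section 10.2 sets the ACC decision rules: at the first stage, of 15 patients, "ACC accrual will be terminated if 7 or more patients are withdrawn from the study after <24 weeks of treatment" (withdrawal of consent excepted), and at the end, with 43 patients, "If the total number responding (defined as stable disease or better) is less than or equal to 24, the drug is rejected". Of the non-ACC patients, Section 10.2 says: "They can be enrolled in any order within the total accrual of 63 patients and will not participate in statistical analysis".

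**The concern.** One text asks for recent progression and the other for progression that is not recent. Neither is superseded: the Study Summary carries the Amendment 8 version and 3.1.2 is the current criterion. The criterion applies to both cohorts and leaves no discretion, so a site cannot resolve the conflict patient by patient.

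Two groups are affected. A patient whose only progression is first seen on the screening scan fits the Summary but fails 3.1.2. A patient whose only progression was long ago fits 3.1.2, which has no outer limit, but fails the Summary.

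The statistical interest lies mainly in the ACC cohort. It is a single-arm test of a null rate of 0.45, with stable disease counted as success and early withdrawal for progression counted towards stopping. With no control arm, the entry criteria define the population to which 0.45 is meant to apply. How recently patients progressed could plausibly affect how many remain stable at either stage. A patient admitted under the unintended window is not removed later on grounds of ineligibility.

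**Working it through.** **The two windows.** Let t be the months from a patient's only qualifying progression to study entry.

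| Source | Accepts |
|---|---|
| Study Summary | 0 ≤ t ≤ 6 |
| Section 3.1.2 | t ≥ 6 |
| Both | t = 6 only |

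A check in steps of 0.1 month from 0 to 24 months found t = 6.0 as the only value that satisfies both.

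**Worked cases (one progression each).**

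| Progression | Study Summary | Section 3.1.2 |
|---|---|---|
| First seen on the screening scan, at most 28 days before treatment (t about 1 or less) | eligible | not eligible |
| t = 2 | eligible | not eligible |
| t = 12 | not eligible | eligible |
| t = 24 | not eligible | eligible |

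**More than one progression.** Both texts need only one event inside the window. A patient with one event more than 6 months ago and another within 6 months meets both. The single-point overlap is therefore a statement about one event, not about every patient.

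**Does anything else reconcile them?** The summary of changes lists edits to 3.1.2 in Amendment 1 (radiation candidacy) and Amendment 4 (limiting that to curative treatment). No entry mentions the six-month window. Sections 6.3 and 10.1.1 describe the ACC population as progressive, which leans towards current disease activity but states no window. The eligibility checklist and eCRF named in Section 11.3 are not among the documents.

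**The design figures.** Section 10.2's figures reproduce with the Simon boundaries of 7 successes in 15 and 24 in 43:

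- Early termination at p = 0.45: P(X ≤ 7 of 15) = 0.6535 (plan 0.654).
- Expected sample size: 15 + (1 − 0.6535) × 28 = 24.70 (plan 24.70).
- Type I error: 0.0481 (plan 0.048).
- Power at p = 0.65: 0.8035, so type II error is 1 − 0.8035 = 0.1965, or 0.196 before rounding the power (plan 0.196).

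Those boundaries count successes, whereas the first-stage text counts withdrawals; that is a separate matter. None of these figures uses the progression window, and the documents do not say which kind of patient the 0.45 describes. They neither support nor weaken the point, and they give no way to size it.

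**The case against.** The strongest reply is that the protocol does identify an operative text. Section 3.0 says eligibility is judged by the criteria in Section 3, and the Study Summary is only a synopsis, so on paper 3.1.2 governs. That is correct, and it narrows the point: a binding criterion contradicts the plan's own summary. It does not remove it, because the literal reading of the binding text is the one that turns away patients with only recent progression.

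A second reply is that the practical reach is unknown. Any one event qualifies, the third event type is broad, neither text gives a reference time for the 20% growth, and patients with several progressions may meet both windows. Central confirmation before registration (Section 11.3) may also have applied one window uniformly. All of this stands. The documents do not show how many patients are affected or which wording was used.

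A third reply is that any effect on the primary test is conjecture. It is right that neither size nor direction can be given. The case for correction rests on the contradictory text, not on a computed bias.

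Two refinements also stand. Sections 2.1, 6.2 and 6.8 limit efficacy analyses to patients who were dosed and re-evaluated, so Section 10.3 is not the only rule on who is analysed; still, none of these would drop a treated, re-evaluated patient for ineligibility. And although the non-ACC cohort is outside the statistical test, it has its own closure rule (more than 2 of the first 10 withdrawn before 24 weeks), so the entry window could matter there too.

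**Conclusion.** The contradiction is real, current and unreconciled, and it sits in a mandatory criterion that cannot be waived. For any patient with a single qualifying progression at a time other than exactly 6 months before entry, the two texts give opposite answers. This rests on reading both sentences literally and on both counting back to the same study entry date. A drafting slip is plausible, but the documents do not establish which window was intended, and this review does not choose one. No effect on type I error, power or either cohort's stopping rule is claimed. The point needs correction because the entry criterion and the summary cannot both be followed.

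**What to change.** The sponsor should confirm the intended window and use that one wording in both Section 3.1.2 and the Study Summary. The eligibility checklist and eCRF should then be checked against it. If patients have already been enrolled, the date of each qualifying progression should be taken from source records so that those outside the confirmed window can be identified. Their ineligibility alone would not remove them from the analysis under Section 10.3.

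The text change is one phrase, but it needs an amendment with the local, institutional, regulatory and BMS approvals listed in Section 11.2. There are two downsides. Patients who meet only the discarded window become ineligible. If enrolment has begun, the cohort may already combine patients admitted under two rules. The documents do not give enrolment status, so the size of that task is unknown.

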3.2 Exclusion Criteria

3.2.1 Patients must not have had chemotherapy ≤ 28 days or radiotherapy ≤ 7 days prior to study treatment.

NOTE: See section 4.6.1 for further clarification on palliative radiotherapy.

3.2.2 Patients who have not recovered to \leq Grade 1 or tolerable Grade 2 from adverse events due to agents administered ≥ 28 days earlier are not eligible.

3.2.3 Patient must not be a candidate for curative surgical or radiation therapy.
NOTE: Palliative radiotherapy is permitted.

3.2.4 Patients may not be receiving any other investigational agents \leq 28 days prior to study treatment.

3.2.5 Patients who have had prior exposure to immune checkpoint inhibitors are not eligible. Please contact principal investigator, for specific questions on potential interactions.
NOTE: Immune checkpoint inhibitors working through OX40 are an exception (for example, MEDI6383, MEDI6469, MEDI0562, oxelumab, and PF-04518600) and are permitted \geq 28 days prior to study registration.

3.2.6 Patients with active autoimmune disease or history of autoimmune disease that might recur, which may affect vital organ function or require immune suppressive treatment including chronic prolonged systemic corticosteroids (defined as corticosteroid use of duration one month or greater), should be excluded. These include but are not limited to patients with a history of:

- immune related neurologic disease
- multiple sclerosis
- autoimmune (demyelinating) neuropathy
- Guillain-Barre syndrome
- myasthenia gravis
- systemic autoimmune disease such as SLE
- connective tissue diseases
- scleroderma
- inflammatory bowel disease (IBD)
- Crohn's
- ulcerative colitis
- patients with a history of toxic epidermal necrolysis (TEN)
- Stevens-Johnson syndrome
- anti-phospholipid syndrome

NOTE: Subjects with vitiligo, type I diabetes mellitus, residual hypothyroidism due to autoimmune condition only requiring hormone replacement, psoriasis not requiring systemic treatment, or conditions not expected to recur in the absence of an external trigger are permitted to enroll.

3.2.7 Patients who have an uncontrolled intercurrent illness including, but not limited to any of the following, are not eligible:

- Ongoing or active infection (including minor localized infections) requiring oral or IV treatment
- Symptomatic class 3 or 4 congestive heart failure, defined as a clinical syndrome resulting from any structural or functional cardiac disorder that impairs the ability of the ventricle to fill with or eject blood
- Unstable angina pectoris
- Cardiac arrhythmia
- Psychiatric illness/social situations that would limit compliance with study requirements
- Any other illness or condition that the treating investigator feels would interfere with study compliance or would compromise the patient's safety or study endpoints

NU Study Number: NU 16N03
BMS Study Number: CA 209-802

3.2.8 Patients should not have any condition requiring systemic treatment with corticosteroids (>10mg daily prednisone equivalents) or other immunosuppressive medications within 14 days prior to first dose of study drug.

NOTE: Inhaled or topical steroids and adrenal replacement steroids at any dose are permitted in the absence of active autoimmune disease. A brief (less than 3 weeks) course of corticosteroids for prophylaxis (eg, contrast dye allergy) or for treatment of non-autoimmune conditions (e.g., delayed-type hypersensitivity reaction caused by a contact allergen) is permitted.

3.2.9 Female patients who are pregnant or nursing are not eligible.

3.2.10. No other prior malignancy is allowed except for the following:

- adequately treated basal cell or squamous cell skin cancer,
- in situ cervical cancer,
- or any other cancer from which the patient has been disease free for at least three years.

3.2.11. Known history of testing positive for human immunodeficiency virus (HIV) or known acquired immunodeficiency syndrome (AIDS) is not permitted.

3.2.12. Any known positive test for Hepatitis B or Hepatitis C virus indicating acute infection is not permitted.

3.2.13. Patients who received a live, attenuated vaccine \leq 30 days before study treatment or are anticipated to require such a live attenuated vaccine are not eligible.

NOTE: Influenza vaccination should be given during influenza season only (approximately October to March). Patients must not receive live, attenuated influenza vaccine (e.g., FluMist) \leq 30 days prior to study registration or at any time during the study.

